 - c. *H2_c: Relative to historical matched controls drawn from previous years of the program, participants receiving sessions will demonstrate greater reductions in HIV sexual risk behavior.*
- 3) **Secondary Aim:** Estimate the effect of MoodGym on the uptake/adherence to ART and PrEP among HIV-positive and HIV-negative participants, respectively.
 - a. *H3_a: Increased attendance to sessions will be associated with lower comorbid depression scores which, in turn, will be associated with increased likelihood of ART medication uptake and/or adherence for HIV-*

positive participants as well as increased likelihood of PrEP uptake and/or adherence for HIV-negative participants.

INTRODUCTION

[figure not shown]
Background

Each year, 70% of new HIV infections in the United States occur with MSM,¹ and use is identified as a major driving force in the continued HIV/AIDS pandemic affecting MSM communities.² Though studies have consistently demonstrated associations between use and HIV transmission among MSM,^{3,4} recent research has further illustrated that depression is likely an under-recognized mechanism in the /HIV link, statistically both mediating and moderating the link between use and engagement in sexual risk behaviors.⁵ Further, depression is an obstacle to medication adherence for both HIV-positive and HIV-negative MSM; depression has been associated with reduced adherence to ART medication,^{6,7} and MSM in the iPrex study with the highest levels of depression also demonstrated the lowest levels of PrEP adherence,⁸ highlighting the important effects of depression on biobehavioral efforts to limit HIV transmission among MSM.

STUDY DESIGN

This study is a single-arm, non-randomized pilot study. Eligible participants are newly enrolled Getting Off service program participants who will be invited to participate in the study during their enrollment, and can enroll in the study at any time during their first two weeks of program participation (see Figure 1).

Figure 1: Study Design “Depression Intervention to Optimize Methamphetamine Treatment Outcomes among Gay and Bisexual Men”

Study activities will take place contemporaneously with participation in the service program (i.e., participants enroll during their first or second week of Getting Off, and

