Specific statistical analyses will be chosen based on the distributional properties of the variables being analyzed; sociodemographics or other variables found to significantly influence primary outcomes may be tested for inclusion as statistical controls and/or bases for contingency analyses. The outcome of primary analytical interest, i.e., engagement in HIV sexual risk behaviors, is most amenable to analyses employing the negative binomial or logistic link functions, for count and dichotomous operationalizations, respectively. Descriptive statistics will be provided for all variables, and inferential models related to Specific Aim 2 will assume three complementary but parallel analytical approaches. First (H2_a), an observed treatment effects dosage response analysis will test for observed associations between attendance to the weekly sessions and reductions in both the magnitude (negative binomial) and/or likelihood (logistic) of engagement in HIV sexual risk behaviors [note: sexual risk behavior data is gathered during standard *Getting Off* procedures]; analyses will be double-robustly estimated to ensure proper model specification.¹¹ Second (H2_b), the same model will be estimated, but will further include participants' CESD-R depression scores both as a main effect, as well as in a statistical interaction term with the number of sessions attended. Planning such a nested analysis allows for full specification of the effects of depression, both directly and in response to the intervention. Third (H2_c), participants' HIV sexual risk behavior outcomes will be statistically contrasted against those same outcomes from a group of historical matched controls sampled from the program (2009-2017) and matched using either caliper or nearest neighbor algorithm (based on method of best fit)¹² using participant age, race/ethnicity, HIV status, and the severity of their use. The proposed Secondary Aim will be tested using the Bernoulli family and logistic link function, where uptake or satisfactory (i.e., $\geq 85\%$) adherence to ART/PrEP during the course of the intervention will be coded a "1", "0" otherwise, and regressed on intervention exposure and/or CESD-R depression scores.

Missing Data

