General Estimation Equation (GEE) analyses will test patterns of missing data in the follow-up assessments. Follow-up assessment data will be coded trichotomously (i.e., observed, intermittent missing, missing due to dropout) and regressed on arm assignment and relevant covariates (e.g., racial/ethnic identity, age) to ensure appropriate application of inferential logic. If a non-ignorable pattern of missing data is discovered (note: confirmed by Little's test of non-random missingness), sensitivity analyses will be conducted to ascertain which missing data management strategy (e.g., multiple partial imputation) should be applied.

DATA COLLECTION AND CONFIDENTIALITY

MoodGym Online Modules

The online modules do not report any sensitive data related to participants' mental health. All usage measures will be based on the recording of the modules completed by each participant during weekly sessions, and depression symptoms and trends are assessed via the weekly CESD-R assessments.

Study Counselor-Administered Assessments

The will briefly assess participants' depression symptoms (via the CESD-R) at the

beginning of each weekly session, and HIV-related medication uptake/adherence (via the ART and PrEP Uptake and Adherence form) at baseline and 3 month follow-up. In both cases, assessments will be administered via an online data entry form administered from the same computer the sessions are accessed. The online data entry form and short-term data hosting will be contracted using Qualtrics, a global data entry firm Friends Research Institute has ongoing multi-year contracts providing access to online survey creation and implementation software. The Qualtrics' system is HIPAA compliant and conforms to industry standard (e.g., ISO 27001 and FEDRAMP compliant) encryption and data security. Study data will be hosted on the Qualtrics cloud for the duration of the study, and will be removed at the completion of the data collection phase.

MONITORING AND ADVERSE EVENT REPORTING

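### Little's test cannot confirm non-ignorable missingness, yet the plan uses it to decide whether missing-data sensitivity analyses are run

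*Combined protocol and SAP*

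**What the plan says.** The Missing Data section under Statistical Considerations is the only text on missing data. It sets out two steps.

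- Screen: "General Estimation Equation (GEE) analyses will test patterns of missing data in the follow-up assessments". Each assessment is classed as seen, missed intermittently or lost through dropout, and this status is "regressed on arm assignment and relevant covariates (e.g., racial/ethnic identity, age".
- Trigger: "If a non-ignorable pattern of missing data is discovered (note: confirmed by Little's test of non-random missingness), sensitivity analyses will be conducted". Their stated purpose is "to ascertain which missing data management strategy (e.g., multiple partial imputation) should be applied".

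The section does not say what is done when nothing is confirmed. It does not define the imputation method that it gives as an example, and it names no MNAR model and no test level. It also does not say which follow-up assessments it covers.

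Two other places bear on this. Study Design states "This study is a single-arm, non-randomized pilot study". Statistical Analyses makes sexual risk behavior the outcome of primary interest and notes that "sexual risk behavior data is gathered during standard" program procedures. For H2_c, that section says these outcomes are "contrasted against those same outcomes from a group of historical matched controls sampled from the program (2009-2017".

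**The concern.** The rule asks a test of MCAR to certify MNAR. A non-significant result in about 42 men could then be taken as clearance, although it is no evidence against MNAR. A significant result could be reported as confirmed non-ignorable missingness when the mechanism is in fact ignorable.

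It is plausible, though the documents do not say so, that men with higher current risk are more likely to miss follow-up. That is the situation an MNAR check is meant to examine, and the plan does not commit to one under either test result. The point bears on the sexual-risk outcome only if the undefined follow-up assessments include it.

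A smaller fault lies in the screen. With one arm, arm assignment takes a single value for every participant, so it cannot predict missingness among them. If study participants versus historical controls was meant, the text does not say so.

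**Working it through.** The plan gives no attrition rate, test level or other figure on this point, so there is nothing of its own to reproduce. The main argument is logical; the simulation only illustrates it.

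**1. What the two steps can see.** Let X be baseline data, Y the follow-up outcome and M = 1 if Y is missing.
- MCAR: P(M=1 | X, Y) is constant.
- MAR: P(M=1 | X, Y) = P(M=1 | X).
- MNAR: P(M=1 | X, Y) still depends on Y once X is given.

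The data identify the distribution of Y given X among those observed. They hold no information on Y given X among those missing. MAR and MNAR differ only in that second distribution. Little's statistic compares observed means across missingness patterns:

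d² = Σ_j n_j (ȳ_j − μ̂_j)ᵀ Σ̂_j⁻¹ (ȳ_j − μ̂_j), with df = Σ_j p_j − p,

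where j indexes patterns, p_j is the number of variables observed in pattern j, and μ̂_j and Σ̂_j are the matching parts of the maximum-likelihood estimates. It uses observed values only, and so does a GEE regression of missingness status on covariates. Joining the two adds nothing about the unseen values.

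**2. What follows from each result.**
- Not confirmed: no sensitivity analysis and no stated handling method.
- Confirmed: sensitivity analyses of unstated content, whose purpose is to choose a strategy.

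**3. Illustration: Little's test alone.** From the documents: n = 42 (Timeline, Table 1; 6 per month × 7 months = 42). Assumed: one follow-up, bivariate normal data, correlation 0.2-0.5, 20-30% missing, 5% level. Missingness follows logit P(M=1) = a + bX (MAR) or a + bY (MNAR), with b = 0.5, 1.0 or 1.5 per SD. Here df = (2 + 1) − 2 = 1. There were 6,000 runs per setting, and rejection under MCAR was 5%.

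| Slope b | Rejects, MAR | Rejects, MNAR | Error of MAR-based mean under MNAR: test rejects | Same: test does not reject |
|---|---|---|---|---|
| 0.5 | 22-29% | 6-11% | 0.08-0.15 SD | 0.08-0.13 SD |
| 1.0 | 64-75% | 7-24% | 0.13-0.24 SD | 0.13-0.25 SD |
| 1.5 | 87-95% | 9-37% | 0.18-0.33 SD | 0.18-0.32 SD |

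Repeat simulations with the same inputs agreed, with the smallest error nearer 0.06 SD. Under MAR the error was 0.03 SD or less. Within the MNAR rows, the test result says almost nothing about how wrong the MAR-based mean is.

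**4. Sensitivity to the assumptions.** A second set-up used three measures, slope 1.5, 20% or 40% missing and 1,500 runs per setting. The test rejected in 4-5% of MCAR and 77-93% of MAR data sets. Under MNAR it rejected in 4-6% at correlation 0, 14-16% at 0.3 and 39-51% at 0.6. The MNAR maximum therefore rises to about 50%. The error was 0.14-0.23 SD with 20% missing and 0.27-0.42 SD with 40%.

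**5. The two-step rule.** Suppose the first step uses only a covariate unrelated to risk and to missingness, tested at 5%. Both steps then reject in roughly:
- MAR: 0.05 × 0.22 = 1.1% to 0.05 × 0.95 = 4.8%.
- MNAR: 0.05 × 0.06 = 0.3% to 0.05 × 0.37 = 1.9%.

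Direct simulation gave similar figures: about 1-5% and 0.3-2.5%. Other covariates would give other rates.

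**The case against.** The strongest reply is that the authors used non-ignorable loosely, to mean not MCAR. On that reading the plan promises sensitivity analyses once MCAR is rejected, under a heading that points toward MNAR, with one method given only as an example. Much of this stands. A reader might infer that the plan rules out an MNAR analysis, or that its named method is ordinary MAR imputation. The documents support neither. The method is undefined, and because dropout is coded apart from intermittent missingness, partial may mean that the two are handled differently. The loose reading still leaves the non-rejection branch with no method and the rejection branch with no specified analysis.

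A second reply is that the percentages describe Little's test and not the plan's rule, which requires a pattern to be found by GEE first. That is correct, as step 5 of the working shows. It is also fair that rejecting more often under MAR at a matched slope is largely built in, since the same slope is put on a seen rather than an unseen variable.

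A third reply is that no planned analysis has been shown to be biased. That stands too. The SD errors are for the mean of a normal outcome, whereas the plan uses negative binomial or logistic models, an interaction and a matched contrast.

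Finally, this is a small pilot of feasibility, acceptability and potential utility. That argues for one simple sensitivity analysis rather than a set of them. It does not justify keeping a rule that cannot do what it says.

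**Conclusion.** The rule is wrong as written and should be corrected. This rests on the null hypothesis of Little's test and on both steps using observed data alone, and needs no numerical assumption. That the arm term is uninformative among participants is equally certain, but minor.

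The size is only illustrative. Under the assumed inputs, rejection by Little's test is a poor guide to MNAR at n = 42, and a MAR-based mean under MNAR is off by about 0.06-0.33 SD whether or not the test rejects. The range moves with correlation, missing rate and slope, none of which the documents give.

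A reader might go on to infer a particular bias in H2_a, H2_b or H2_c. The documents do not support that. They give no attrition figure and do not say whether the risk outcome falls under this section. They also do not describe missingness in the historical controls, and similar missingness there could cancel an error in the H2_c contrast. Further, the hypothesis is worded as "participants receiving sessions will demonstrate greater reductions in HIV sexual risk behavior" while the analysis text contrasts outcomes, and any error would depend on which of the two is compared.

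**What to change.** 1. Remove Little's test as the trigger and delete the wording that it confirms a non-ignorable pattern. The test may stay as a description of the data.
2. State which follow-up assessments the section covers, and say explicitly whether the sexual-risk outcome is among them.
3. State a MAR-based default for missing sexual-risk outcomes, using baseline risk, the matching covariates (age, race/ethnicity, HIV status, severity of use) and sessions attended.
4. Pre-specify one simple MNAR sensitivity analysis for the sexual-risk outcome, for example delta-adjusted imputation over a range of departures fixed before analysis. Run and report it whatever any test shows.
5. Minor: replace arm assignment with sessions attended when modelling missing sexual-risk or ART/PrEP follow-up. If study versus historical controls is meant, say so, and use that indicator only if missingness is recorded for the controls.

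The cost is SAP wording and a modest amount of extra analysis, including fixing the range for item 4 in advance. No new data are needed and recruitment does not change.

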complete the 5 sessions over the remaining 6-7 weeks). If participants complete all five MoodGym modules prior to the 8-week endpoint, they will be offered the chance to revisit prior module(s); assessments and incentives will continue as scheduled. Getting Off program evaluation data from study participants will be matched and compared with historical program evaluation data to assess the impact of the MoodGym intervention on the Getting Off program outcomes through an observed treatment effects analysis.

MoodGym

MoodGym is a seven module computer-optimized, evidenced-based intervention for adults with depression and/or anxiety symptoms. Though MoodGym modules can be taken by participants without assistance, evidence suggests results may be improved by applying in a more structured setting. In this pilot study, MoodGym will be delivered with support and guidance from a trained Study Counselor. Each week participants will be asked to attend one one-hour individual appointment with the Study Counselor to complete a MoodGym module, for up to seven weeks.

Phone Call After One Missed Session of MoodGym

The SC will monitor participant attendance and conduct a phone call to any participant who does not attend a scheduled session, to reschedule.

SELECTION AND ENROLLMENT OF PARTICIPANTS

Inclusion Criteria

- A participant enrolled in the Getting Off service program at Friends Community Center; and,
- Within his first or second week in the program

Exclusion Criteria

- Not a participant in his first or second week of the Getting Off service program at Friends Community Center

STUDY PROCEDURES

Recruitment and Enrollment

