MoodGym Implementation					X	X	X	X	X	X	X	X	X
Data Cleaning & Analysis													X
Begin Publication & Dissemination													X

STATISTICAL CONSIDERATIONS

Assessments

1. Center for Epidemiologic Studies Depression Scale (Revised). The Center for Epidemiologic Studies Depression Scale (Revised) [CESD-R]⁹ is a widely used depression assessment which consistently shows strong psychometric properties and concurrent validity with clinical diagnostic instruments.¹⁰ The CESD-R will be administered at the start of each session.

2. ART and PrEP Uptake and Adherence. Administered at baseline enrollment in the pilot study and 3-month follow-up only. The ART and PrEP Uptake and Adherence form briefly queries HIV-positive and HIV-negative participants as to whether they have begun and/or adhered to a prescribed ART or PrEP regimen in the past 3 months.

Statistical Analyses

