Adverse event reporting will follow the WIRB policies. Serious adverse events (SAEs) include any of the following outcomes for the participant: 1) death; 2) acute life-threatening incidents; 3) hospitalization or the prolongation of a hospitalization; or 4) persistent or significant disability. SAEs events may be communicated to the principal investigator by participants or staff, or may be observed directly by the principal investigator. SAEs will be reported regardless of whether they are considered study-related.

Distress Policy

In the instance of:

- 1) a participant presenting with a gun or other weapon, and/or threatening physical violence against staff, himself, or an identified other person;
- 2) a family member or friend of a participant informing a staff member that a participant is threatening to harm staff, himself, or an identified other person;

the Friends Community Center *Distress Protocol for Participants at Friends Community Center* is automatically triggered. Staff immediately contact a trained counselor or clinician to assess the situation and advise management. Staff are provided with a phone tree providing the names and contact information (including mobile phones and pagers) for six trained counselors/clinicians familiar with, and who have agreed to carry out, the Friends Community Center *Distress Protocol*. In the case of extreme immediate threat, staff are trained to remove themselves, immediately dial 911, and to ensure the safety of themselves, other staff, and participants above all else.

Regulatory Updates

The principal investigator will report any information related to unanticipated risks or new information that may change the risk-benefit ratio to the WIRB IRB. This information may come from the current study or findings from other studies. Any changes in the protocol or consent as a result of this information will be promptly reported to the WIRB and CHIPTS. The Principal Investigator will also report any irregularities in the conduct of the study such as: participant enrollment; obtaining informed consent; and, data collection and processing.

HUMAN PARTICIPANTS

Institutional Review Board (IRB) Review and Informed Consent

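### No listed study contact asks about serious adverse events and no collection window is set, so the SAE count is a lower bound that probably depends on attendance

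*Combined protocol and SAP*

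**What the plan says.** Monitoring and Adverse Event Reporting opens with "Adverse event reporting will follow the WIRB policies"; those policies are not reproduced. It then defines the events ("Serious adverse events (SAEs) include any of the following outcomes for the participant"), listing death, acute threats to life, admission to hospital or a longer stay, and lasting or significant disability. On how events become known, it says "SAEs events may be communicated to the principal investigator by participants or staff, or may be observed directly by the principal investigator". It adds that "SAEs will be reported regardless of whether they are considered study-related".

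The study contacts are described elsewhere:

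- **Weekly session** (Assessments; MoodGym Intervention): "The CESD-R will be administered at the start of each session", followed by an online module.
- **Missed-session call** (Phone Call After One Missed Session of MoodGym): the Study Counselor will "conduct a phone call to any participant who does not attend a scheduled session, to reschedule".
- **ART/PrEP form** (Assessments): "Administered at baseline enrollment in the pilot study and 3-month follow-up only".

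The Distress Policy covers weapons and threats of harm, including self-harm: "Staff immediately contact a trained counselor or clinician to assess the situation and advise management".

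**The concern.** The protocol describes how an SAE might reach the principal investigator, but gives nobody the task of asking. It also does not say when collection begins and ends, or whether it continues for a man who has stopped attending. Death, a life-threatening incident or a hospital admission would usually happen away from the center and would itself interrupt attendance. The men with an event may therefore be among those least likely to be seen.

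Two things are at stake: oversight of men in treatment for methamphetamine use who are also receiving a depression intervention, and the safety record this pilot leaves behind. The study has a single arm, so no concurrent group would show up under-capture.

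**Working it through.** The documents state no SAE rate, dropout rate or safety analysis, so there is no planned figure to reproduce. The check is a reading of each contact, followed by an illustration of scale.

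**1. Does any listed contact ask about SAEs?**

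- Weekly session: CESD-R, module, and as much counselor interaction as the participant initiates. No SAE item is listed.
- Missed-session call: the stated purpose is rescheduling. No SAE item is listed.
- Baseline and 3-month contact: the ART/PrEP form only. No SAE item is listed.
- No SAE form, observation window or safety tabulation appears anywhere in the document.

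**2. Does capture depend on attendance?**

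- Recruitment and Enrollment lists follow-up interviews among the in-person contacts at the center. Study Counselor-Administered Assessments says the ART/PrEP form is entered on the computer used for sessions. As described, the 3-month contact needs a return to the center.
- Incentive Schedule pays \$10 for each of up to seven sessions, to a total of \$70. Since 7 × 10 = 70, nothing is left for the 3-month form.
- Missing Data has a category for dropout, so the plan expects some, but gives no rate.
- Routes not tied to study sessions do exist. Service-program staff may see the man, since the study runs alongside the program, and relatives or friends may alert staff to threats of harm. Neither route is set up to ask about SAEs.
- The Distress Policy, as summarized in this protocol, shows no step passing an activation to the principal investigator for event assessment.

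**3. Scale (illustration only).** Input from the Timeline table: n = 42 (6 a month × 7 months). Assumed: a true risk p that a man has an SAE, and a probability s that it is captured, independent between men.

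Upper limit with zero recorded SAEs, one-sided 95%: 1 − 0.05^(1/42) = 6.9% at full capture. Dividing by s gives the limit on the true risk: 6.9/0.75 = 9.2%, 6.9/0.5 = 13.8%, 6.9/0.25 = 27.5% (from the unrounded 6.884%).

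Chance of recording zero SAEs: (1 − p·s)^42.

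| True risk p | Expected men with an SAE (42p) | s = 100% | s = 75% | s = 50% | s = 25% |
|---|---|---|---|---|---|
| 2% | 0.84 | 42.8% | 53.0% | 65.6% | 81.0% |
| 5% | 2.1 | 11.6% | 20.1% | 34.5% | 59.0% |
| 10% | 4.2 | 1.2% | 3.8% | 11.6% | 34.5% |

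A 10% risk captured half the time gives the same chance of a zero count (11.6%) as a 5% risk captured fully. Without knowing s, the count cannot separate the two.

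**The case against.** The strongest reply is that the protocol's wording is permissive, not exclusive. It says events may be communicated or observed, and does not say these are the only routes. Reporting is placed under IRB policies we cannot see, and a requirement to ask could sit there. The consent pages are also unavailable. A man who stops MoodGym has not necessarily left the service program, whose staff are a named route to the principal investigator; he is also due a call and a 3-month follow-up. All of this stands. It means SAEs *may* be missed, not that they will be.

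A reader might also infer that the promise to report SAEs whatever their relation to the study is contradicted. It is not. That sentence says known events are not filtered by causality; it does not promise complete ascertainment.

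A reader might infer that the Distress Policy loses events. The center's full distress protocol is not reproduced, and a threat of self-harm is not one of the four SAE outcomes. All that can be said is that no onward step appears here.

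Finally, no aim, hypothesis or analysis uses an SAE count, and even perfect capture in 42 men leaves an upper limit of 6.9% after zero events. Better collection would not turn a zero into strong evidence of safety. That limits the weight of the point, but does not answer the gap: none of the contacts the protocol describes asks the question, and no window is stated.

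**Conclusion.** The point holds in a limited form. SAE ascertainment is described as passive, no listed contact asks about the four outcomes, and no collection window is set. Capture therefore probably depends on attendance and on volunteered reports.

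It would be going too far to call the count uninterpretable. It is a valid minimum, but it cannot be read as a low rate. The number of SAEs that might be missed cannot be derived from the documents; the figures in the working rest on assumed risks and capture shares and show direction and scale only.

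The consequence is for safety oversight and reporting, not for any planned inference. The conclusion assumes that the unseen IRB policies and service-program procedures do not already require systematic questioning; if they do, the protocol should say so. The change is worth making because it is cheap.

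**What to change.** - Add one fixed question covering the four listed SAE outcomes to the weekly session form, the missed-session call script and the 3-month form, with the date of any event.
- State the collection window as consent to the 3-month contact, for every enrolled man whatever his attendance.
- Report SAEs with the number of men and the person-time actually ascertained, and the number lost to contact. This matters because a question gets no answer from a man who has died or cannot be reached; the report should show how many men the count does not cover.

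The cost is one item on existing forms and on the call script, with no new visit or staff. Contacts become slightly longer, and the reported SAE count will probably be higher, which should be expected and not taken as a signal in itself. No planned analysis changes.
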